7.3 Lost to Follow-Up

A participant will be considered lost to follow-up (LTFU) if he or she fails to return and is unable to be contacted by the study site staff for up to 180 days following his/her final visit or call.

The following actions must be taken if a participant fails to return to the clinic for a required study visit:

- The site will attempt to contact the participant and reschedule the missed visit within the visit window, and ascertain if the participant wishes to and/or should continue in the study.
- Before a participant is deemed lost to follow-up, the investigator or designee will make every effort to regain contact with the participant (where possible this will include 3 telephone call attempts and, if necessary, a certified letter to the participant's last known mailing address or local equivalent methods). These contact attempts should be documented in the participant's medical record or study file.

Since the participant may be incapacitated, the LAR will be contacted in the event the participant cannot be reached.

Should the participant continue to be unreachable with no known outcome, he or she will be considered to have withdrawn from the study with a primary reason of lost to follow-up.

8 STUDY ASSESSMENTS AND PROCEDURES

8.1 Efficacy Assessments

8.1.1 Day 0 – Start of TMZ Treatment Cycle 1

- Patients will begin treatment with temozolomide at 4 weeks (+14 days) from end of radiotherapy.
- Cycle 1 will be dosed at 150mg/m² daily for 5 consecutive days of a 28-day cycle.
- Optune therapy should start within two weeks of start of adjuvant temozolomide, but not more than 7 weeks from the end of temozolomide/RT and will be continuous throughout study.
- Review Concomitant Medications
- Update Adverse Events

8.1.2 Week 4 (-3/+7 days) - Start of Subsequent TMZ Treatment Cycles, repeat every 4 weeks up to 12 cycles

- Physical Exam
- Patients will begin treatment with temozolomide cycle 2 and subsequent cycles every 4 weeks (-3/+7 days) at 200 mg/m², if the CTC non-hematologic toxicity for Cycle 1 is Grade ≤2 (except for alopecia, nausea and vomiting), absolute neutrophil count (ANC) is ≥ 1.5 x 10⁹/L, and the platelet count is ≥ 100 x 10⁹/L.
 - The dose remains at 200 mg/m² per day for the first 5 days of each subsequent cycle unless toxicity occurs. If the dose was not escalated at Cycle 2, escalation should not be done in subsequent cycles.
- Neurological status and KPS
- CBC with differential
- Biochemistry Panel (electrolytes, creatinine, bilirubin, liver enzymes)
- Steroid Dose (recorded)
- Optune therapy will be continuous throughout study. Compliance documentation will be obtained every 4 weeks (-3/+ 7 days).
- Review Concomitant Medications
- Update Adverse Events

8.1.3 Week 8 (+/- 1 week) – repeat MRIs every 8 weeks only, until treatment stop

- Contrast-enhanced MRI of the brain
- Quality of life questionnaires (EORTC QLQ-C30/BN20, and MMSE)
- RANO assessment
- Review Concomitant Medications
- Update Adverse Events

8.1.4 Progression

If progression is identified, the following procedures should be performed:

- Contrast-enhanced MRI of the brain
- Physical Exam
- Neurological status and KPS
- CBC with differential
- Steroid Dose (recorded)
- Biochemistry panel (Electrolytes, creatinine, bilirubin, liver enzymes)
- Quality of life questionnaires (EORTC QLQ-C30/BN20, and MMSE)
- RANO assessment
- Optune Therapy – confirm continuation (See Recommendations for Use of Optune)
- Optune Compliance
- Review Concomitant Medications
- Update Adverse Events
- Tumor Tissue sample – determining availability of FFPE, pathology slides and/or frozen sample(s) for first recurrence

8.2 Safety and Other Assessments

The following labs are collected for safety by the investigator or his/her designee:

- CBC with differential
- Pregnancy Test (urine or serum) – WOCBP only
- Biochemistry (electrolytes, creatinine, bilirubin, liver enzymes)

Lab results should be reviewed promptly.

8.2.1 After Treatment Stop

Week 4 (+/- 7 days) from treatment stop

The following will be performed 4 weeks (+/- 7 days) from treatment stop:

- Physical exam
- Neurological status and KPS
- CBC with differential
- Biochemistry Panel (electrolytes, creatinine, bilirubin, liver enzymes)
- Review Concomitant Medications
- Update Adverse Events

8.2.2 Survival Follow-up

Every 3 months +/- 14 days

After the final visit is conducted, subjects will be followed every 90 days (3 months) +/- 14 days, either by phone or in-person.

See the Survival Follow-up Telephone Script for specific questions.

8.3 Adverse Events and Serious Adverse Events

8.3.1 Definition of Adverse Events (AE)

Adverse event means any untoward medical occurrence associated with the use of an intervention in humans, whether or not considered intervention-related (21 CFR 312.32 (a)).

8.3.2 Definition of Serious Adverse Events (SAE)

An adverse event (AE) or suspected adverse reaction is considered "serious" if, in the view of either the investigator or sponsor, it results in any of the following outcomes: death, a life-threatening adverse event, inpatient hospitalization or prolongation of existing hospitalization, a persistent or significant incapacity or substantial disruption of the ability to conduct normal life functions, or a congenital anomaly/birth defect. Important medical events that may not result in death, be life-threatening, or require hospitalization may be considered serious when, based upon appropriate medical judgment, they may jeopardize the participant and may require medical or surgical intervention to prevent one of the outcomes listed in this definition. Examples of such medical events include allergic bronchospasm requiring intensive treatment in an emergency room or at home, blood dyscrasias or convulsions that do not result in inpatient hospitalization, or the development of drug dependency or drug abuse.

8.3.3 Classification of an Adverse Event

8.3.3.1 Severity of Event

AEs will be assessed according to the CTCAE version 5.0 (term and grade) and documented. If CTCAE term does not exist, the PI should select the most appropriate CTC category and indicate "other".

If CTCAE grading does not exist for an AE, the severity of the AE will be graded as:

1. Mild - Events require minimal or no treatment and do not interfere with the participant's daily activities.
2. Moderate - Events result in a low level of inconvenience or concern with the therapeutic measures. Moderate events may cause some interference with functioning.
3. Severe – Events interrupt a participant's usual daily activity and may require systemic drug therapy or other treatment. Severe events are usually potentially life-threatening or incapacitating. Of note, the term "severe" does not necessarily equate to "serious"
4. Life-threatening

5. Fatal

8.3.3.1.1 CEREBRAL EDEMA TOXICITY EXCEPTION:

NCI CTCAE criteria categorize all cerebral edema as grades 3-5. Cerebral edema, with or without mass effect, normally presents in glioma patients as part of the disease process and can be exacerbated by standard of care chemotherapy and radiation. Therefore, cerebral edema, for purposes of this protocol, although ranked grades 3-5 by NCI CTCAE criteria, will be graded with the full range of toxicities in order to accurately capture the AE: (1) Mild (2) Moderate (3) Severe (4) Life Threatening (5) Fatal.

8.3.3.1.2 CLINICAL SIGNIFICANCE OF LAB RESULTS

Only clinically significant lab abnormalities will be recorded as AEs.

Abnormal laboratory results shall be assessed by the Site investigator (or designee) promptly for clinical significance. Laboratory reports should be initialed and dated by the evaluator.

An abnormal lab value should be deemed clinically significant if both of the following conditions are met:

- The abnormality suggests a disease and/or organ toxicity that is new or has worsened from baseline.
- The abnormality is of a degree that requires additional active management, e.g., change of dose, discontinuation of the drug, close observation, more frequent follow-up assessments, or further diagnostic investigation.

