2.1.3.1.2 POTENTIAL ADVERSE EVENTS: TEMOZOLOMIDE

Treatment with temozolomide commonly (>30%) causes the following adverse events:

- Headache
- Fatigue
- Nausea
- Vomiting
- Constipation

Treatment with temozolomide commonly (10-30%) causes the following adverse events:

- back, abdominal and/or stomach pain, breast pain
- diarrhea
- alopecia (hair loss)
- dry skin, skin redness, itching and/or rash,
- erythema multiforme (a skin condition that is similar to a bad rash)
- swelling of extremities (arms, legs, fingers, or toes)
- inflammation or swelling of the mouth, throat and/or sinuses
- confusion, amnesia, dizziness, fever, and/or weakness
- anxiety, depression
- joint and muscle pain
- hemiparesis
- asthenia
- coordination abnormal
- viral infection
- insomnia
- changes in sense of taste
- changes in vision such as double or blurred vision
- coughing or shortness of breath, respiratory tract infection
- urinary incontinence/frequency, urinary tract infection
- weight increase

- seizures, hemiparesis (weakness on one side of the body)
- adrenal hypercortisim (elevated hormone levels)
- allergic reactions, sometimes severe
- hepatotoxicity
- lymphopenia, thrombocytopenia, neutropenia, and leukopenia
- anorexia
- convulsions
- Very rare side effects have included secondary cancers (including leukemia and myelodysplastic syndrome (MDS))

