3 OBJECTIVES AND ENDPOINTS

TABLE 2: OBJECTIVES & ENDPOINTS

OBJECTIVES	ENDPOINTS	JUSTIFICATION FOR ENDPOINTS
Primary		
To determine whether TTFIELDS combined with adjuvant temozolomide increases OS in patients with newly diagnosed Grade II and III astrocytoma with TERT promoter mutation only compared to historical and contemporaneous controls.	OS measured in days from Study Day 0 until death. If the study ends and the participant is still living, OS will be measured in days from Study Day 0.	OS remains the primary concern within this patient population. Intent to Treat analysis will be used to determine if this objective is met.
Secondary		

 To determine whether the combination of TTFIELDS and adjuvant temozolomide is safe in the newly diagnosed high-risk Grade II and III astrocytoma. To determine whether TTFIELDS combined with adjuvant temozolomide increases PFS in patients with newly diagnosed Grade II and III astrocytoma with TERT promoter mutation only compared to historical and contemporaneous controls. To evaluate QOL using KPS, EORTC QLQ-C30/BN20, and MMSE in patients treated with TTFIELDS combined with adjuvant temozolomide compared to 	
 PFS measured in days from Day 0 to progression Safety measured by incidence and severity of Adverse Events and Toxicities. Quality of life measured by KPS, EORTC QLQ-C30/BN20, and MMSE Correlation between % Compliance with TTFIELDS and OS 	Safety, Efficacy, and Quality of Life measures for a more complete view of the effects of the study treatment(s).

historical and contemporaneous controls.		
Tertiary/Exploratory		

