10.4 Safety Analyses

Clinical and laboratory test parameters monitored for the purpose of identifying severe adverse events (SAEs) will be summarized at the end of the trial using standard summary statistics and confidence intervals. The cumulative incidence of SAEs will be monitored continuously within the framework of a stopping rule.

Stopping Rule: We will use separate sequential Pocock-type boundaries [82] to monitor continuously for chemotherapy-related and device-related SAEs. If the cumulative number of patients experiencing an SAE is equal to or exceeds the relevant boundary indexed by the number of patients currently enrolled, a halt in enrollment will be triggered for further evaluation, to determine if the study should be discontinued for safety reasons.

The maximum acceptable toxicity rate will be set at 25% for device-related SAEs, and 50% for chemotherapy-related SAEs.

Each type of SAE will have its own boundary, which will be specified so that the overall probability of stopping the trial early for each type of SAE is 0.05 when the true device-related rate is less than 25% or the true chemotherapy-related rate is less than 50%.

TABLE 11: POCOCK BOUNDARY STOPPING RULE FOR DEVICE-RELATED SAE MONITORING

(SAE target rate=25%, N=90 patients in the treatment arm)

Number of Patients	1	2	3	4	5	6	7	8	9	10	11	12	13	14	15	16	17	18	19	20
SAE Boundary	-	-	-	4	5	5	6	6	7	7	7	8	8	9	9	9	10	10	10	11
Number of Patients	21	22	23	24	25	26	27	28	29	30	31	32	33	34	35	36	37	38	39	40
SAE Boundary	11	11	12	12	13	13	13	14	14	14	15	15	15	16	16	16	17	17	17	18
Number of Patients	41	42	43	44	45	46	47	48	49	50	51	52	53	54	55	56	57	58	59	60
SAE Boundary	18	18	19	19	19	20	20	20	21	21	21	22	22	22	23	23	23	23	24	24
Number of Patients	61	62	63	64	65	66	67	68	69	70	71	72	73	74	75	76	77	78	79	80
SAE Boundary	24	25	25	25	26	26	26	27	27	27	28	28	28	28	29	29	29	30	30	30
Number of Patients	81	82	83	84	85	86	87	88	89	90										
SAE Boundary	31	31	31	32	32	32	32	33	33	33										

(Stop trial if cumulative number of patients experiencing a device-related SAE is equal to or exceeds the SAE event boundary)

TABLE 12. POCOCK BOUNDARY STOPPING RULE FOR CHEMOTHERAPY-RELATED SAE MONITORING

(SAE target rate=50%, N=90 patients in the treatment arm; will be expanded to include contemporaneous controls if enrolled)

Number of Patients	1	2	3	4	5	6	7	8	9	10	11	12	13	14	15	16	17	18	19	20
SAE Boundary	-	-	-	-	-	-	7	8	9	10	10	11	12	12	13	14	14	15	15	16

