11.1.9 Data Handling and Record Keeping

11.1.9.1 Data Collection and Management Responsibilities

Data collection is the responsibility of the clinical trial staff at the site under the supervision of the site investigator. The investigator is responsible for ensuring the accuracy, completeness, legibility, and timeliness of the data reported.

All source documents should be completed in a neat, legible manner to ensure accurate interpretation of data.

Hardcopies of the study visit worksheets will be provided for use as source document worksheets for recording data for each participant enrolled in the study. Data recorded in the electronic case report form (eCRF) derived

from source documents should be consistent with the data recorded on the source documents. It is permissible to use site worksheets or EMR records in place of visit worksheets if the same information is documented.

Clinical data (including adverse events (AEs), concomitant medications, and expected adverse reactions data) and clinical laboratory data will be entered into REDCap, a 21 CFR Part 11-compliant data capture system provided by the University of Florida Coordinating Center. The data system includes password protection and internal quality checks, such as automatic range checks, to identify data that appear inconsistent, incomplete, or inaccurate. Clinical data will be entered directly from the source documents.

Data should be entered into REDCap, including uploading related source documents, within 14 days of data collection.

For urgent data transmissions (Serious Adverse Events, etc.), fax and/or secure email transmission is acceptable with separate notification to the Coordinating Center confirming receipt of the records for review.

[contact]

Separate notification via email: *[contact]* or via [contact].

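### Laboratory toxicity becomes a graded AE only if the site judges that it needs active management, and Section 10.4 names no CTCAE-graded laboratory table, so some Grade 3-4 values can be missing from the safety results

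*Combined protocol and SAP*

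**What the plan says.** Table 2 in Section 3 defines the secondary safety endpoint: "Safety measured by incidence and severity of Adverse Events and Toxicities". It asks for severity, and it names toxicities as well as AEs.

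Section 8.3.3.1.2 decides which laboratory findings enter the AE record: "Only clinically significant lab abnormalities will be recorded as AEs". The test has two parts, and both must be satisfied: "An abnormal lab value should be deemed clinically significant if both of the following conditions are met". The first part is a new or worsened disease or organ toxicity. The second reads: "The abnormality is of a degree that requires additional active management, e.g., change of dose, discontinuation of the drug, close observation". The list of examples goes on to more frequent visits and further diagnostic work-up.

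Section 8.3.3.1 grades AEs by CTCAE v5.0. Sections 8.3.4.1 and 8.3.9 require all AEs of Grade 3 and above to be collected.

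Section 10.4 gives the only planned laboratory analysis: "Clinical and laboratory test parameters monitored for the purpose of identifying severe adverse events (SAEs) will be summarized at the end of the trial", by standard summary statistics and confidence intervals. It mentions no grade, worst value or shift from baseline.

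The raw material is collected. A CBC with differential and a biochemistry panel are scheduled every 4 weeks on treatment (Table 1, Section 8.1.2), and Section 11.1.9.1 says that "clinical laboratory data will be entered into REDCap".

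**The concern.** The endpoint asks how often toxicity occurs and how severe it is. For laboratory toxicity, the severity grade is attached only after the site has decided that the value needs managing. A count can be Grade 3 or 4 and still not be an AE, and the Grade 3+ entry rule does not then apply to it.

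This bears on secondary objective 1, whether the combination is safe. Section 2.1.3.1.2 names "lymphopenia, thrombocytopenia, neutropenia, and leukopenia" among the harms of temozolomide, so these are foreseen toxicities. With 10-20 centres each deciding what needs management, part of any reported rate would reflect local habit. Section 9.5 collects no AEs from control patients, so no internal comparison would show under-capture.

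**Working it through.** The plan gives no figure to reproduce. The check is to follow an abnormal value through the rules.

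**Step 1: the AE filter.** Section 8.3.3.1.2 sets two conditions, neither of which refers to CTCAE grade. A value that meets the first but is judged to need no added management is not an AE.

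**Step 2: the Grade 3+ rule.** Sections 8.3.4.1 and 8.3.9 apply to AEs, so a value removed at Step 1 never reaches them.

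**Step 3: which values trigger action under the protocol.** A dose change is one of the examples of active management. A value that triggers a dose rule therefore passes the filter.

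| Laboratory value | Protocol rule tied to it | Recorded as a graded AE? |
|---|---|---|
| Neutrophils and platelets past the stated thresholds | Cycle start and dose reduction (6.1.2.4, Table 8); Cycle 2 escalation (6.1.2.3, 8.1.2) | Normally yes |
| Chemistry at Grade 3, if read as non-haematological toxicity | Table 8; Cycle 2 escalation (6.1.2.3, 8.1.2) | Normally yes |
| Lymphocytes, total white cells, haemoglobin | None in 6.1.2.3, 6.1.2.4 or 8.1.2; footnote 8 of Table 1 could reach them in Cycle 1 | Depends on site judgement |

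**Step 4: a conflict that affects the last row.** Footnote 8 of Table 1 makes Cycle 2 escalation conditional on haematologic toxicity below Grade 1 and names no cell line. Sections 6.1.2.3 and 8.1.2 use only the neutrophil and platelet counts. A graded lymphopenia in Cycle 1 therefore has a dose consequence under one text and none under the other. Its AE status can turn on which text a site follows.

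**Step 5: does Section 10.4 fill the gap?** It covers parameters monitored to identify SAEs, an abbreviation it expands as severe although Section 8.3.2 uses it for serious. On either reading it summarises parameters and commits to no grade. A reader could not obtain from it the proportion of patients with a Grade 3-4 lymphocyte count.

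**Step 6: size.** Let P be the true proportion of patients with a given Grade 3-4 abnormality and c the fraction of those patients in whom the site judges that management is needed. The proportion in the AE tables is then P × c. The documents give neither P for Grade 3-4 nor c. As c runs from 1 to 0, the reported figure runs from P to zero. The lower extreme, as a pure assumption: with the 90 treated patients of Section 10.1 and c = 0, the table shows 0/90, with an exact 95% upper limit of 1 − 0.025^(1/90) = 4.0%, whatever the value of P.

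**The case against.** The strongest reply is that active management is defined broadly. Close observation, an extra visit or a repeat test is enough. A lymphopenia that is merely watched more closely qualifies, is graded and must be entered. Section 8.3.2 also lists blood dyscrasias among events that may be judged serious without hospitalisation. This stands. A reader might infer that lymphopenia and leukopenia go unreported even at Grade 3-4, but the text shows only that they can be left out at the site's discretion.

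Three other stronger readings also fail:

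- **All haematological toxicity is lost.** Neutrophil and platelet falls that trigger the dose rules pass the filter (Step 3).
- **Pre-cycle blood draws make the counts look near normal by construction.** Section 6.1.2.4 ties the start of a cycle to neutrophils and platelets only, so it cannot normalise lymphocytes or white cells. The same section bases reductions on the lowest counts of the previous cycle and allows local monitoring, so pre-cycle draws are not the only ones foreseen.
- **The loss can be sized from the 10-30% list in Section 2.1.3.1.2.** That list is not specific to Grade 3-4, and it ends with effects described as very rare. Position in it does not establish an incidence.

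It is also fair that Section 10.4 does plan a laboratory summary, that its wording could include proportions, and that the values are in the database, so a graded table could be produced without any amendment. But the plan does not commit to one, and nothing in the reply supplies a severity result that is independent of site judgement.

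**Conclusion.** The point holds in a limited form. AE status for laboratory values rests on management and not on grade, and no graded laboratory analysis is specified. Grade 3-4 values that a site does not act on can be missing from the graded safety results. The exposure is mainly in lymphocytes, total white cells and haemoglobin, and the reported rate depends partly on site practice.

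The direction is understatement. The size cannot be derived from the documents. It depends on how often sites leave such values without closer observation, follow-up or work-up, and it would be nil if they never do. The primary endpoint, overall survival, is untouched. No between-arm safety comparison is biased, because controls contribute no AEs. The change is worth making because it is cheap and because it replaces a discretionary filter with a reproducible derivation for a stated secondary endpoint.

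**What to change.** In Section 10.4, add a laboratory toxicity analysis that is independent of AE status:

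- Grade every post-baseline CBC, differential and biochemistry value in REDCap by CTCAE v5.0.
- For each parameter, report the worst post-baseline grade per patient, a baseline-to-worst shift table, and the proportion of patients with Grade 3 or higher with an exact 95% confidence interval.
- State that the laboratory toxicity rates in the safety endpoint come from these derived grades. Section 8.3.3.1.2 stays as it is for individual AE reporting.
- State the limitation that scheduled draws are mostly pre-cycle, so the derived rates may still miss mid-cycle nadirs.

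The cost is some wording and a few derived tables, with no new visit, test or patient. Reported laboratory toxicity rates will be the same or higher.

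Separately, the Cycle 2 escalation conditions in footnote 8 of Table 1 and in Sections 6.1.2.3 and 8.1.2 must be reconciled by those responsible for the clinical rules. This review takes no view on which is right.
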